6.2. Diagnosis and Management of Malaria

Patients found to have malaria based on laboratory confirmation will have a second finger prick for a thin smear (to determine parasite species), hemoglobin measurement using a portable spectrophotometer (HemoCue), and collection of plasma, with residual blood used for testing of an experimental hemozoin-based rapid diagnostic test(MOD) or experimental magnetic levitation-based parasite detection (in children only). All episodes of malaria will be classified as uncomplicated or complicated based on the following criteria:

Uncomplicated malaria (all of the following)

- 1) Fever (> 38.0°C tympanic) or history of fever in the previous 24 hours
- 2) Positive thick blood smear
- 3) Absence of complicated malaria

Complicated malaria (any of the following)

- 1) Evidence of severe malaria (Appendix E) and parasitemia
- 2) Danger signs present in children (Appendix E) and parasitemia

Episodes of malaria will also be classified into the following categories according to the timing of previous malaria episodes for treatment purposes:

- New episodes of malaria will be defined as any first episode or any episode occurring > 14 days after the diagnosis of a previous episode
- 2. Treatment failures will be defined as any of the following:
 - a. Complicated malaria occurring 1-14 days after the diagnosis of a previous episode
 - b. Fever (≥ 38.0°C tympanic) or history of fever in the previous 24 hours with a parasite density ≥ the parasite density of an episode of malaria diagnosed 2 days prior
 - c. Fever (≥ 38.0°C tympanic) or history of fever in the previous 24 hours with a parasite density ≥ 25% of the parasite density of an episode of malaria diagnosed 3 days prior
 - d. Fever (≥ 38.0°C tympanic) or history of fever in the previous 24 hours with a positive thick blood smear of any parasite density occurring 4-14 days after the diagnosis of a previous episode

All patients diagnosed with new episodes of uncomplicated malaria will be prescribed AL, the recommended first-line treatment in Uganda for children and pregnant women in their 2nd or 3rd trimester. Patients with complicated malaria will be prescribed quinine or artesunate according to national malaria treatment guidelines. Children who are less than 4 months of age or weigh <5kg, will be treated with quinine for uncomplicated malaria in accordance with the

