Uganda Ministry of Health Guidelines. Patients with treatment failure within 14 days following treatment with AL will be prescribed quinine according to national malaria treatment guidelines. Patients with treatment failure within 14 days following treatment with quinine or artesunate will be treated with quinine plus clindamycin or artesunate.

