8.1.2. Secondary Outcomes

Secondary outcomes are summarized in Table 3 below.

Secondary outcome	Definition
Placental malaria by histopathology	Any evidence of placental infection (parasites or
	pigment)
Placental parasitemia	Proportion of placental blood samples positive for
	parasites by microscopy or LAMP
Maternal malaria	Any treatment for malaria during pregnancy
Incidence of adverse events	Adverse events stratified by type, severity score
	and relationship to study drugs
Prevalence of anemia	Proportion of routine hemoglobin measurements
	< 11 g/dL & < 8 g/dL
Prevalence of asymptomatic	Proportion of routine monthly samples positive
parasitemia	for parasites by microscopy and LAMP

Table 3. Secondary outcomes

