8.1.3. Analyses

A modified intention-to-treat approach to all analyses will be used, including all study participants randomized to therapy and have the outcome of interest measured including all

follow-up time until the study participants complete the study or early study termination regardless of whether the intervention was stopped due to an adverse event.

Primary analysis. We will compare the risk of having any adverse birth outcome between the study arms using the Chi-Square or Fisher's exact test. We will explore for any differences of potential confounders between the treatment arms and if necessary adjust our analysis using multivariate logistic regression. We will also perform sub-group analyses comparing the risks of having individual adverse birth outcome (LBW, preterm delivery, SGA) between the study arms using the Chi-Square or Fisher's exact test.

Secondary analyses. We will compare the prevalence of different definitions of placental malaria (placental parasitemia by microscopy, placental malaria by LAMP, placental malaria by histopathology) using the Chi-Square or Fisher's exact test. We will compare the incidence of maternal malaria and adverse events using Poisson or negative binomial regression models. The Poisson models will include the logarithm of the follow-up time as an offset. We will translate the fitted coefficients and their confidence bounds into percentage effects with the formula 100*[exp(coefficient)-1]. This approach is closely related to exponential survival models for analyzing events per follow-up time, but is better able to adjust for violated assumptions. Testing for overdispersion in the Poisson regression can detect violations of these assumptions, and variances can be adjusted accordingly to produce valid p-values and confidence interval. If significant deviations from required distributions in study data are detected, we will employ negative-binomial or zero-inflated negative-binomial models to account for the observed pattern of data. We will compare the prevalence of maternal anemia and asymptomatic parasitemia using generalized estimating equations with adjustments for repeated measures in the same study participant. If necessary, multivariate analyses will be performed to adjust for potential confounders and effect modifiers.

8.2. Hypothesis 2

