8.2.1. Primary Outcome

The primary outcome will be the incidence of malaria, defined as the number of incident episodes per time at risk. Incident cases will include all treatments for malaria not proceeded by another treatment in the previous 14 days. Time at risk will begin at birth and will end when study participants reaches 12 months of age or early study termination (if prior to 12 months of age).

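### Maternal malaria is counted per treatment with no 14-day rule, so a re-treated treatment failure is two events in a woman but one in an infant

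*Combined protocol and SAP*

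**What the plan says.** Table 3 in section 8.1.2 defines maternal malaria as "Any treatment for malaria during pregnancy". Section 8.1.3 then states: "We will compare the incidence of maternal malaria and adverse events using Poisson or negative binomial regression models". It adds: "The Poisson models will include the logarithm of the follow-up time as an offset". Sections 2.1 and 8.1 also name the outcome as an incidence.

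For infants, section 8.2.1 is explicit about what counts: "Incident cases will include all treatments for malaria not proceeded by another treatment in the previous 14 days" (reading the verb in its evident sense of coming before).

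Section 6.2 covers women and children alike. It sorts episodes "according to the timing of previous malaria episodes for treatment purposes". A new episode is "any first episode or any episode occurring > 14 days after the diagnosis of a previous episode". Recurrences inside that window that meet listed criteria are treatment failures, for example fever or a history of fever "with a positive thick blood smear of any parasite density occurring 4-14 days after the diagnosis of a previous episode". A failure leads to another treatment: "Patients with treatment failure within 14 days following treatment with AL will be prescribed quinine according to national malaria treatment guidelines".

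Nothing in section 8.1 carries the 14-day rule over to women.

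**The concern.** The protocol itself generates second treatments that it does not regard as new episodes, and Table 3 has no rule to stop them being counted. The infant outcome has such a rule, so the trial would report malaria incidence on two different bases.

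Two analysts could also derive different maternal counts from the same records: one taking Table 3 literally, the other borrowing the infant rule. If that choice is made after unblinding, it depends on the data. What is at stake is the exact size of a secondary incidence and its comparability with the infant incidence. The primary birth outcome, the sample size and the safety monitoring are not affected.

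**Working it through.** **One record under each rule.** Take AL on day 0, then fever with a positive smear on day 10, then quinine.

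| Rule | Count |
|---|---|
| Section 6.2 (women and children) | 1 new episode + 1 treatment failure |
| Section 8.2.1 (infant outcome) | 1 incident case |
| Table 3 (maternal outcome), read literally | 2 treatments, so 2 events |

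With AL on day 0 and again on day 40, all three rules give two. The rules differ only for re-treatment inside the 14-day window.

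**Could Table 3 mean ever/never treated?** The word *any* allows it. A Poisson or negative binomial model with log follow-up time as an offset does not fit a yes/no outcome. It models a count, so the literal reading is a count of treatments.

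**Size.** The plan states no figure for this outcome, so there is none to reproduce. Inputs:
- 41 episodes over 43.0 person-years in the 3 dose SP arm of the previous Tororo trial (section 1.2), used as an illustration: 41 / 43.0 = 0.953 per person-year.
- f, the share of episodes re-treated once within 14 days. This is not given for this trial. The nearest documented figure is a 99% AL cure rate in Ugandan pregnant women (section 1.1), which suggests f of about 1%. The values 5% and 10% are assumptions.

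Formulas:
- Count = 41 × (1 + f).
- Rate = count / 43.0.
- Mean events per episode = (1 − f) × 1 + f × 2 = 1 + f. Mean square = (1 − f) × 1 + f × 4 = 1 + 3f. The variance-to-mean ratio for Poisson episodes is therefore (1 + 3f) / (1 + f).

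| f | Count | Rate per person-year | Variance / mean |
|---|---|---|---|
| 0 | 41 | 0.95 | 1.00 |
| 1% | 41.4 | 0.96 | 1.02 |
| 5% (assumed) | 43.1 | 1.00 | 1.10 |
| 10% (assumed) | 45.1 | 1.05 | 1.18 |

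**Rate ratio, DP over SP.** It is multiplied by (1 + f_DP) / (1 + f_SP):
- Equal f in both arms: 1.00, no change.
- 10% with SP and 5% with DP (assumed): 1.05 / 1.10 = 0.95.
- 10% with SP and 0% with DP (assumed): 1.00 / 1.10 = 0.91.

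**The case against.** The strongest reply is that Table 3 is only a summary. The outcome is called an incidence throughout, and the one place where the protocol defines malaria incidence, section 8.2.1, uses the 14-day rule. A sensible analyst might carry it over. That reading is plausible, but Table 3 gives its own definition and section 8.1 does not point to 8.2.1, so the literal count remains what is written. The reply also says rightly that section 6.2 classifies episodes for treatment rather than analysis. The infant outcome is therefore the proper comparator.

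A reader might go further in four ways that the documents do not support:

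- **That the double count biases the comparison towards DP.** Section 8.1.3 reports relative effects, 100 × [exp(coefficient) − 1]. The ratio is unchanged if f is the same in both arms, and the documents give no evidence that it differs. If the previous trial's 41 versus 0 episodes recurred, the ratio would be 0 under either rule. That trial also used 3 dose SP, not the monthly SP given here, so its pattern may not carry over.
- **That paired events make the standard errors too small.** This would hold for an unadjusted Poisson test. Section 8.1.3 plans a check for overdispersion, a variance adjustment, and negative binomial models if needed.
- **That after-hours care routinely adds a second treatment.** Section 6.4 has the hospital supply AL and refer the patient to the study clinic next morning. It does not describe a change of drug.
- **That complicated malaria in Table 4 double counts whenever a child is re-treated.** That row also lacks an interval rule, but a second event arises only if the second treatment again meets the severe-malaria or danger-sign criteria.

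**Conclusion.** The point holds as a small defect in a stated counting rule. As written, Table 3 with section 8.1.3 counts re-treatment of a failing maternal episode as a second event, while section 8.2.1 would count it once in an infant. The inflation is a factor of 1 + f: about 1% on the only documented input, and 5% to 10% on assumed values. The 1% figure assumes that the cited cure rate approximates this trial's chance of re-treatment within 14 days, which the documents do not establish. The calculation also assumes at most one re-treatment per episode. A shift in the rate ratio would need different re-treated shares by arm, which is possible but undocumented. This is a free improvement to a secondary outcome and does not threaten the trial's conclusions.

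**What to change.** In Table 3, define maternal malaria as incident episodes during pregnancy: a treatment counts only if the woman had no other malaria treatment in the 14 days before it, as section 8.2.1 does for infants. Report maternal treatment failures on a separate line. If the intention really is to count every treatment, say so and explain why the infant rule differs.

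Optionally, add to Table 4 that a second treatment within 14 days that again meets the complicated criteria is not a new complicated episode. Progression from uncomplicated to complicated malaria would still count.

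The cost is one or two lines of wording, settled before unblinding. Section 6.2 already requires staff to time each episode against the previous one, so no new data are needed. Sample size, visits and treatment rules stay as they are.

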Two recent studies from East Africa have shown that IPTp with DP is more effective than SP at reducing the risk of malaria during pregnancy and the risk of placental malaria at delivery.^{25,26} However, there were limitations to these studies and WHO policy recommendations continue to recommend the use of IPTp with SP. This proposal will address some of these limitations by using a dosing strategy in-line with updated WHO recommendations, power the study to detect a difference in the risk of adverse birth outcomes, undertake a more thorough assessment of adverse events including repeated assessments of QTc prolongation in all study participant, and assess the impact of different IPTp regimens on the incidence of malaria during infancy. We will perform a randomized, double-blinded, controlled trial to compare IPTp with SP vs. DP delivered every 4 weeks starting as early in the 2nd trimester as possible in an area of high transmission intensity and widespread antifolate resistance. Pregnant women will undergo frequent sampling using a highly sensitive molecular assay to better define the timing and frequency of malaria infection during pregnancy and the primary outcome will be based on a composite adverse birth outcome of low birth weight (LBW), preterm delivery, or small for gestational age (SGA). The overall theme of this proposal will be that in areas of high malaria transmission intensity where the burden of malaria remains high despite the use of currently available control interventions, aggressive and strategic use of highly effective drugs for IPTp may improve birth outcomes and reduce the risk of malaria during infancy.

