To evaluate experimental malaria diagnostic tests during pregnancy and infancy. 1) We will evaluate a Photo-Thermal Reader with the Ugandan public sector's primarily used rapid diagnostic test (RDT), CareStart Pf HRP-2, and an experimental, highly-sensitive HRP2-based RDT to detect malaria parasites during pregnancy. We will estimate the sensitive and specificity of the Photo-Thermal Reader using a standard RDT and an experimental, highlysensitive RDT using quantitative PCR (qPCR) as the gold standard. RDT results will be used for research purposes only and not for clinical care. 2) We will evaluate the relative performance of a hemozoin-based rapid diagnostic test versus Ugandan public sector's primarily used Rapid Diagnostic Test (RDT), CareStart Pf HRP-2, and an experimental, highly-sensitive HRP2based RDT to detect malaria parasites in infants. We will estimate the sensitivity and specificity of the Magneto-Optical Detection (MOD) test using standard RDT and microscopy test , using quantitative PCR (qPCR) as the gold standard. All results will be used for research purposes only and not for clinical care.

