CareStart Pf HRP-2 (Access Bio Inc USA) RDT testing using the PTS reader will be performed at enrollment and every 4 weeks at the time of routine visits during pregnancy. Approximately 5 μ L of whole blood will be placed on the cartridge, which is inserted into the reader, and the reader will take approximately 1-3 minutes to complete the testing. The graphical user interface (GUI) guides the user through the assay process. Quantitative PCR will be performed at enrollment and at the time of routine visits using standardized procedures on \sim 100ul of whole blood. A HRP2-based experimental RDT will be tested at enrollment and every 8 weeks at the time of routine phlebotomy during pregnancy using \sim 100ul of whole blood. An RDT result will be considered positive if both the control line and the test line are visible after the development time. A result will be considered negative if the control line is visible, but no test line appears. The result will be considered invalid if no control line is visible, regardless of whether or not a test line appears. A hemozoin-based experimental rapid diagnostic test (MOD) will be performed at routine visits in a subset of children using ~ 50ul of whole blood collected by finger prick or phlebotomy. Approximately 50ul of whole blood will be placed in a special cuvette with a custom dilute, which is inserted into the sonicator and then the reader, and it will take approximately 2 minutes to complete the testing. For samples undergoing parasite detection by magnetic levitation, less than 10 µL of blood will be mixed with a paramagnetic

agent such as gadolinium, placed in close proximity to the earth magnets, and visualized by microscopy and/or a magnified imaging system.

Procedures for reporting and follow up of incidental concerning metabolite testing results Participants will be considered at elevated risk for Sickle Cell Disease (SCD) or Congenital Hypothyroidism (CH) according to the following criteria:

 SCD: Patterns of adult hemoglobins [HbA(A) and variants (S,C,D,E, B-thal)] as well as hemoglobin peak percentages (HGB-FAST, HGB-F1, HGB-F, HGB-F+F1, HGBFAST+ F1, HGB-Other, HGB-A] based on the interpretation of the lowa testing laboratory.

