8.2.2. Secondary Outcomes

Secondary outcomes are summarized in Table 4 below.

···· ··· ···	
Secondary outcome	Definition
Incidence of complicated malaria	Any treatment for malaria meeting criteria for
	severe malaria or danger sings
Incidence of hospital admissions	Admission to the pediatric ward for any cause
Infant mortality rate	Any deaths occurring after birth
Prevalence of anemia	Proportion of routine hemoglobin measurements
	< 10 g/dL & < 8 g/dL
Prevalence of asymptomatic	Proportion of routine samples (by microscopy or
parasitemia	LAMP) positive for asexual parasites.

Table 4. Secondary outcomes

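### Table 3 defines maternal asymptomatic parasitaemia by microscopy *and* LAMP, at odds with the *or* used for placenta and infants, and gives the scheduled maternal qPCR no role in the outcome

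*Combined protocol and SAP*

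**What the plan says.** Four places in the combined protocol and SAP bear on this outcome.

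- **Outcome definitions.** Section 8.1.2, Table 3 counts routine monthly maternal samples positive "for parasites by microscopy and LAMP". In the same table, placental parasitaemia is the proportion of placental blood samples positive for "parasites by microscopy or LAMP". In section 8.2.2, Table 4, the infant counterpart begins "Proportion of routine samples (by microscopy or" and goes on to name LAMP.
- **Analysis.** Section 8.1.3 says "We will compare the prevalence of maternal anemia and asymptomatic parasitemia using generalized estimating equations", with adjustment for repeated measures. It names no assay.
- **Assays scheduled.** Section 6.10.4 states: "Quantitative PCR will be performed at enrollment and at the time of routine visits". Section 6.5 and the Appendix G schedule agree: qPCR at enrolment and at each 4-weekly visit from week 16 to week 40. LAMP is listed in section 6.10.4 as one of several methods, joined by *and/or*, that may be applied to filter-paper blood collected with each thick smear.
- **Purpose.** The Rationale (section 1.3) says "Pregnant women will undergo frequent sampling using a highly sensitive molecular assay", so as to describe when and how often infection occurs in pregnancy. It does not name the assay. Objective 4 (section 2.4) evaluates experimental diagnostic tests "using quantitative PCR (qPCR) as the gold standard".

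**The concern.** The conjunction decides what the outcome measures. If a sample must be positive on both tests, the measured prevalence cannot exceed the microscopy prevalence, and the molecular test can only remove positives. Low-density infections found by LAMP but missed on the smear would be counted as no infection. Those are the infections that the Rationale and the background on point-of-care testing say the trial wants to detect.

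If the row instead lists two measures, there are two maternal parasitaemia results and no statement of which one carries the comparison between arms. With qPCR also run at the same visits, at least four versions are open: both positive, either positive, each method separately, or qPCR. A choice made once results are known would be open to selection.

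**Working it through.** **1. The plan's own figure.** None exists. Section 8.4 gives no expected prevalence, sample size or power for this outcome, so there is nothing to reproduce.

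**2. The definitions side by side.**

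| Outcome | Place | Rule |
|---|---|---|
| Maternal asymptomatic parasitaemia | Table 3 | microscopy *and* LAMP |
| Placental parasitaemia | Table 3 | microscopy *or* LAMP |
| Infant asymptomatic parasitaemia | Table 4 | microscopy *or* LAMP |
| Any section 8 outcome using qPCR | Tables 3 and 4 | none |

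**3. How much the conjunction could matter.** The only paired smear and molecular prevalences in the documents are in section 1.2: placental blood in a cross-sectional study of 565 women, 17.5% positive by smear and 28.1% by PCR. PCR stands in for LAMP here, and placental blood for routine maternal blood. Both are assumptions. With marginal prevalences S = 17.5% and M = 28.1%:

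- Both positive: at most min(S, M) = 17.5%. The lower limit is max(0, S + M − 100%) = 0%.
- Either positive: at least max(S, M) = 28.1% and at most S + M = 45.6%.
- Share of molecular positives kept under a both-positive rule: at most 17.5/28.1 = 0.623, or 62%. Share lost: at least 1 − 0.623 = 37.7%.
- Gap between the two rules: at least 28.1 − 17.5 = 10.6 percentage points.

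**4. Does it threaten power?** Section 1.2 gives parasite prevalences in the earlier trial of 40.5% (3 dose SP) and 5.2% (monthly DP), with no assay stated. Take 391 × 0.95 ≈ 371 women per arm, one sample per woman, a two-sided 5% test, and the same share of positives kept in both arms:

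| Share kept | SP | DP | Power |
|---|---|---|---|
| 100% | 40.5% | 5.2% | about 100% |
| 62% | 25.2% | 3.2% | about 100% |
| 30% | 12.2% | 1.6% | above 99.9% |
| 10% | 4.1% | 0.5% | about 90% |

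The comparison stays well powered unless almost all positives are lost. An equal share kept leaves the prevalence ratio unchanged (40.5/5.2 = 7.8) and shrinks the difference. At 62% kept, the difference falls from 40.5 − 5.2 = 35.3 points to 25.2 − 3.2 = 22.0 points. The control arm in that trial was 3 dose SP, not the monthly SP used here, so these inputs are illustrative too.

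**The case against.** The strongest reply is that *and* here lists two measures and sets no joint condition. The anaemia row of Table 3 joins its 11 and 8 g/dL cut-offs with an ampersand. A both-required rule there would make the higher cut-off redundant, so two prevalences must be meant. Section 8.1.3 likewise treats the placental tests one by one despite the *or* in Table 3: "We will compare the prevalence of different definitions of placental malaria (placental parasitemia by microscopy, placental malaria by LAMP", followed by histopathology. On that reading LAMP alone captures smear-negative infection and nothing is lost. This is plausible, and it rules out saying that the plan definitely discards submicroscopic infections, as a reader might infer from the literal wording. It does not settle the point: the row can still be read either way, no maternal measure is named as the main one, and qPCR still has no stated role.

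A reader might also infer that the protocol names qPCR as the gold standard for this outcome, so that LAMP is wrong. The documents do not say that. The label belongs to the diagnostic evaluation in Objective 4. LAMP is itself molecular and could be the unnamed sensitive assay of the Rationale. Using one assay to compare treatments and another to judge diagnostic tests is not an error in itself. Choosing qPCR is a recommendation, resting on its being scheduled at every routine maternal visit.

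**Conclusion.** The definition is ambiguous, and it conflicts with the two sister definitions. Its literal reading gives the least sensitive version of the outcome, against the stated purpose of the maternal sampling. The reference assay scheduled at the same visits is left out of the treatment comparison. This should be corrected before analysis. It concerns one secondary outcome and does not touch the primary outcome or the sample size.

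The loss in this trial cannot be computed, because the documents give no smear versus LAMP or qPCR figures for routine maternal blood. The loss of at least 38% of molecular positives holds only under the both-positive reading and on the two stand-in assumptions.

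Two further inferences are not supported. One is that the comparison between arms is biased or underpowered: no bias is shown, and power is ample in the illustration. The other is that mothers and infants can no longer be compared: they fall under separate hypotheses with separate analyses, and no maternal-infant comparison of parasitaemia is planned.

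**What to change.** Replace the Table 3 row with one of the following, and name the chosen measure in section 8.1.3 as the one the generalized estimating equations will use.

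- **Preferred:** *Proportion of routine 4-weekly samples positive for parasites by qPCR (main definition); proportion positive by microscopy reported separately.*
- **If LAMP is kept:** *Proportion of routine 4-weekly samples positive for parasites by microscopy or LAMP; each method also reported separately.* This matches the placental row and Table 4. Add a sentence saying what role, if any, qPCR has in this outcome.

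The cost is SAP wording. Neither version needs new sampling, since qPCR and filter-paper collection are both scheduled at the routine maternal visits. The preferred version has a small downside: the main maternal assay may differ from the one named for infants. Appendix H has no qPCR column, although section 6.5 lists qPCR among the infant tests at 12, 28 and 52 weeks. Any maternal LAMP results can be shown as a sensitivity analysis.
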